1046 If it is felt that the febrile reaction is potentially associated with BCG, the blind will be broken for that patient and, if the patient was assigned to the BCG-treated group, a 1047 1048 determination will be made as to whether antituberculosis therapy should be prescribed. 1049 1050 Acute, severe illnesses potentially associated with BCG-treatment should be aggressively 1051 treated with isoniazid (300 mg), rifampin (600 mg), and ethambutol (1,200 mg) daily for 1052 six months and further BCG treatments discontinued. Sepsis, the most severe 1053 complication, may be treated with isoniazid (300 mg), rifampin (600 mg), and ethambutol (1,200 mg), and cycloserine (500 mg) twice daily. At the discretion of the 1054 principal investigator, prednisone (40 mg) may be prescribed intravenously and acutely. 1055 For acute severe illness, consultation with an Infectious Disease Specialist is required. 1056 1057 1058 **11.6 Premature Termination** 1059 1060 In the event that a patient terminates from the study prior to week 34 or week 68, every 1061 effort should be made to obtain follow-up efficacy and safety data which should include 1062 the following: 1063 1064 Concomitant medications 1065 Physical examination 1066 Urinalysis 1067 Urine culture 1068 CBC with electronic differential, RBC's, Platelets 1069 Voiding diary collected 1070 Follow-up symptoms 1071 IC symptom and Problem Index 1072 RAND SF-36 1073 MOS Sexual Functioning Scale 1074 University of Wisconsin Symptom Survey 1075 Adverse experiences 1076 Serum B-HCG (women of child-bearing potential only) and assessment of 1077 current birth control methods 1078 1079 The Clinical Center Stop Point or "STOP" CRF should also be filled out for these 1080 patients, indicating the reason for termination.

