## **BCG ACCIDENT INSTRUCTIONS**

**Eye Splash:** Flush affected eyes) with copious amounts of water for at least 15 minutes while holding the eyelids) open; then seek evaluation by a physician.

**Skin Exposure/Self-Inoculation:** In case of skin contact with the drug, exposure of open sores, or finger laceration, thoroughly wash affected area with soap and water and clean wound with alcohol.

In case of suspected, accidental self-inoculation, PPD skin testing is advised at the time of the accident and six weeks later in order to detect skin test conversion. Asymptomatic skin test conversion is equivalent to BCG vaccination and does not require anti-tuberculous medication.

Skin test conversion should, however, be evaluated by a physician.

NOTE: If finger stick or laceration should develop granulomatous lesion of the skin, treatment may be given with isoniazid (300 mg/day) and continued for two weeks after wound has healed.

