## **ORGANON TEKNIKA**

In patients who develop persistent fever or experience an acute febrile illness consistent with BCG infection, two or more antimycobacterial agents should be administered while diagnostic evaluation, including cultures, is conducted. **BCG treatment should be discontinued**. Negative cultures do not necessarily rule out infection. Physicians using this product should be familiar with the literature on prevention, diagnosis, and treatment of BCG-related complications and, when appropriate, should consult an infectious disease specialist or other physician with experience in the diagnosis and treatment of mycobacterial infections.

TICE®BCG is sensitive to the most commonly used antituberculous agents (isoniazid, rifampin and ethambutol). **TICE®BCG is not sensitive to pyrazinamide**.

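### The sepsis regimen in Section 11.5 does not say whether *twice daily* applies to all four drugs or to cycloserine only, and it gives no duration

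*Protocol*

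**What the plan says.** Section 11.5 of the protocol (Management of Associated Adverse Events and Discontinuation of Treatment) sets out two antituberculosis regimens in consecutive sentences.

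- **Acute, severe illness possibly due to BCG.** Patients are to be "treated with isoniazid (300 mg), rifampin (600 mg), and ethambutol (1,200 mg) daily for" six months, and further BCG is stopped. One frequency stands after three drugs, and a duration is given.
- **Sepsis.** It "may be treated with isoniazid (300 mg), rifampin (600 mg), and ethambutol (1,200 mg), and cycloserine (500 mg) twice daily". The first three drugs and their milligram figures are the same. Cycloserine is added, one frequency stands at the end, and there is no duration.

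Shortly afterwards the section adds a safeguard: "For acute severe illness, consultation with an Infectious Disease Specialist is required".

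The protocol touches on drug treatment of BCG infection elsewhere, but gives no other dosed regimen for sepsis. The package insert in Appendix H says that in suspected BCG infection "two or more antimycobacterial agents should be administered while diagnostic evaluation, including cultures, is conducted", without doses or frequencies. Appendix G (BCG Accident Instructions) mentions isoniazid for a skin lesion in a healthcare worker: "treatment may be given with isoniazid (300 mg/day) and continued for two weeks after wound has healed".

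**The concern.** The two sentences are built alike. In the first, the single closing frequency has to apply to every drug, because no drug has one of its own. A reader who carries that construction into the next sentence applies *twice daily* to all four drugs, and so doubles the daily amount of the three that have just been given once a day. The text calls sepsis the most severe complication, so such a reader could take the higher frequency as deliberate escalation.

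A reader who attaches the closing frequency to cycloserine alone meets a different problem. The sepsis sentence then gives no frequency for isoniazid, rifampin or ethambutol, and one has to be borrowed from a regimen written for another condition.

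What is at stake is patient safety at nine clinical sites. This is the only dosed sepsis regimen in the document, and it would be consulted in an emergency. Non-responders may also receive a further six instillations of BCG in Phase 2. The point has no bearing on sample size, power or the primary analysis.

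**Working it through.** The plan has no daily total to reproduce, so the check is a reading of the two sentences and one multiplication per drug.

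**Inputs (all from Section 11.5).** The stated doses are isoniazid 300 mg, rifampin 600 mg, ethambutol 1,200 mg and cycloserine 500 mg. The first three figures are identical in both sentences. The closing frequency is once daily in the acute-illness sentence and twice daily in the sepsis sentence.

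**Formula.** Daily total = mg per administration × administrations per day.

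**Acute severe illness.** Isoniazid 1 × 300 = 300 mg; rifampin 1 × 600 = 600 mg; ethambutol 1 × 1,200 = 1,200 mg.

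**Sepsis, reading A: the closing frequency covers all four drugs.** Isoniazid 2 × 300 = 600 mg; rifampin 2 × 600 = 1,200 mg; ethambutol 2 × 1,200 = 2,400 mg; cycloserine 2 × 500 = 1,000 mg.

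**Sepsis, reading B: the closing frequency covers cycloserine only.** Cycloserine 2 × 500 = 1,000 mg. The other three have no frequency in this sentence. If the once-daily schedule of the preceding sentence is assumed to carry over, they are 300, 600 and 1,200 mg.

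| Drug | Reading A, mg/day | Reading B, mg/day | A ÷ B |
|---|---|---|---|
| Isoniazid | 600 | 300 (assumed) | 2.0 |
| Rifampin | 1,200 | 600 (assumed) | 2.0 |
| Ethambutol | 2,400 | 1,200 (assumed) | 2.0 |
| Cycloserine | 1,000 | 1,000 | 1.0 |

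**Duration.** Six months is stated for acute severe illness and nothing for sepsis. Under either reading, no drug in the sepsis sentence has a stated duration.

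**Does another part of the protocol settle the frequency?** No.

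- Appendix H names classes and agents but gives no antituberculosis doses or frequencies.
- The isoniazid 300 mg/day in Appendix G is for a skin lesion after a finger stick or laceration in staff, so it cannot be used to interpret a sepsis regimen in patients.
- The published method cited in Section 11.5 is for febrile reactions, and its content is not reproduced in the protocol.

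**The case against.** Three arguments on the other side carry weight.

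**The syntax leans towards the milder reading.** The sepsis sentence is not a plain list of four. A conjunction before ethambutol closes a three-drug series, and a second conjunction then appends cycloserine with its frequency. That favours attaching *twice daily* to cycloserine alone. This stands, and it means that the doubled regimen is not the single literal meaning of the text. It does not give the other three drugs a frequency.

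**The two sentences concern different conditions.** A reader might infer that Section 11.5 contradicts itself, or that it orders double doses in sepsis. The document supports neither inference. Two conditions may properly have two regimens, and the only thing unclear is how far one modifier reaches. The lower totals also rest on an assumption, since they require the once-daily schedule to be borrowed from the sentence before.

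**There are safeguards.** The sepsis wording is permissive. Consultation with an infectious-disease specialist is required for acute severe illness, which reasonably includes sepsis. Section 11.5 also advises consulting the site's infectious-disease physician for serious events possibly or probably associated with BCG. Section 9.1 allows isoniazid only after withdrawal, unblinding and a decision that antituberculosis therapy is needed. Section 3.1 adds that BCG sepsis had not been seen in interstitial cystitis patients to date. All of this makes it less likely that a clinician would act on the sentence alone. None of it says which reading is meant.

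**Conclusion.** The point holds as an ambiguity in a safety instruction. The sepsis sentence does not show whether its one frequency covers four drugs or one, and it omits a duration. The two readings differ by a factor of 2.0 in the daily totals of isoniazid (300 v 600 mg), rifampin (600 v 1,200 mg) and ethambutol (1,200 v 2,400 mg). They agree on cycloserine. The lower figure in each pair assumes that the daily schedule carries over from the preceding sentence.

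The repeated conjunction favours the cycloserine-only reading, but under that reading the instruction is incomplete for three drugs. Permissive wording and specialist consultation lower the risk without resolving the text. Correction is still worthwhile, because this is the protocol's only dosed regimen for its gravest complication. No view is taken here on which dose, frequency or duration is right.

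**What to change.** The sponsor should reconcile the two consecutive sentences in Section 11.5 and rewrite the sepsis sentence so that each of the four drugs carries its own frequency and duration. The values should be confirmed by the sponsor's infectious-disease advisers; none is proposed here. The cost is a one-sentence correction. Randomisation, endpoints, sample size and analysis are untouched.

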## **12 ADMINISTRATIVE SECTION**

### **12.1 Institutional Review Board**

It is the responsibility of the Principal Investigator to provide the appropriate Institutional Review Board (IRB) with all pertinent material, including a copy of the informed consent. Approval of the protocol and the informed consent form must be obtained and forwarded to the sponsor prior to screening or enrolling any subjects. The Investigator also maintains the responsibility of initiating protocol re-approval, notification of protocol and/or consent form changes, notification of adverse reactions, and termination of the study according to the appropriate IRB requirements. A suggested consent form is included in Appendix A.

### **12.2 Laboratory Accreditation**

The Principal Investigator must maintain documentation of adequate licensure or accreditation for all clinical laboratory facilities used for study samples analysis. In addition, the clinical laboratory's normal values for test results must be forwarded to the DCC prior to study initiation. This documentation should cover the entire period the protocol is active.

## 12.3 Sponsor Monitoring/On-site Monitoring

 The progress of the study will be carefully monitored by an experienced site-monitoring firm, for compliance with applicable government regulations and protocol. These individuals will have access to all records necessary to ensure integrity of the data and the regulatory documents at the clinical sites.

## 12.4 Compliance with Agencies

The sponsor will ensure this study is performed in compliance with applicable regulations associated with the Food and Drug Administration (FDA), the International Conference on Harmonization (ICH) (42)Guidelines and the Declaration of Helsinki. The sponsor will also keep a 1572 (Statement of Investigator), and current CVs of all Principal Investigators and Co-Investigators on file.

### 12.5 Record Retention

 The DCC must maintain all study records for a period of time in accordance with their internal SOPs and applicable regulations. The study site must retain source records, including original Patient Consent Forms, until either the sponsor or DCC notifies them in writing.

# 11241125 **12.6 Direct Access to Source Documents**

Investigators will maintain, on-site, in an orderly fashion, and make available to the sponsor or the sponsor's representative, the following documents: the signed study protocol, amendments, informed consent documents, investigator brochure, approval letters from the IRB, drug accountability forms, CRFs, all primary source documentation, and all letters of correspondence.

11321133

1126

## 12.7 Data Management and Analysis

1134

The Data Coordinating Center (DCC) will coordinate all ICCTG activities pertaining to:

1135 1136 1137

1138

1139

- 1. Design, development, production, testing and distribution of case report forms (CRFs) over the internet to the client workstations at each clinical center;
- 2. Collection, entry, verification, validation and query resolution of data; and
- 3. Quality assurance monitoring and reporting.

1140 1141

Data management issues, especially those concerning data quality and integrity in multicenter trials, as discussed extensively in Meinert (43) DeMets (44) Neaton (45) Bailey (46), and McFadden (47), will be addressed within the Manual of Procedures (MOP) and emphasized during the Research Coordinator (RC) training prior to protocol initiation.

1147

- 1148 The DCC will develop and maintain a computerized Data Management System (DMS)
- for this ICCTG Protocol, that will be deployed on client workstations within each of the
- 1150 Clinical Centers. Case report forms (CRFs) will be available to be printed locally at the
- clinical centers from Portable Data Files (PDF). Originals of these forms will be retained
- by the clinical sites. Double data entry will be performed at the Clinical Centers,
- 1153 utilizing the DMS tools available on the clients' workstations. In particular, for the
- Baseline Visit 2, there will be a manual back-up system for implementing randomization
- of participants, in the event the DMS system is not functional at the moment that a new
- randomization is required.

1157

- Validation checks will be performed at the centralized database to verify data accuracy
- and identify missing, unclear, illogical, or problematic responses. Queries will be generated to resolve discrepancies. Confidentiality will be strictly adhered to by
- assigning a unique participant identifier that will not identify the subject by name. The
- 1162 Manual of Procedures will define these processes in detail.

1163

- Details describing the transfer of urine specimens between the clinical sites and the
- 1165 ICCTG associated laboratories are presented in the Appendix E.

## 13 STATISTICAL CONSIDERATIONS

### **13.1 Study Design**

The proposed study design is a two-arm, double-blind, randomized clinical trial (RCT) to evaluate the effect of intravesical BCG, compared to intravesical saline placebo on IC symptoms. The primary analysis on which sample size requirements are based is the comparison of response rates for the composite primary outcome as defined in Section 4.4.1. For this comparison, we desire adequate numbers of participants to detect a difference in response rates between 30% and 50% (difference of 20%).

The primary endpoint for which the comparative efficacy of BCG and saline will be evaluated is a composite endpoint with two components: a) the patient-reported global assessment of response and b) the use of specified breakthrough medications for IC symptoms during the last four weeks of the follow-up period. The global evaluation of improvement for the primary endpoint will occur at week 34 or withdrawal, whichever comes first, relative to IC symptoms at baseline, via the question:

"As compared to when you started the study, how would you rate your Interstitial Cystitis (IC) symptoms now?"

A seven point scale, centered at zero, will be used, with categories as follows: -3) markedly worse; -2) moderately worse; -1) slightly worse; 0) no change; +1 slightly improved; +2) moderately improved; and +3) markedly improved. Participants who answer either +2) moderately improved or +3) markedly improved on the global evaluation are considered to have evidence of "clinical improvement", and will be classified as a "responder" for the global assessment portion of the primary endpoint.

The second component of the primary endpoint relates to changes (increase or addition) in the use of IC treatment medications from the level at which the patient was stabilized at the beginning of the study, and the use of "breakthrough" medications. Increased usage of pre-study IC medications, or the initiation of new IC medications, during the last four weeks of post-treatment follow-up (weeks 31 - 34 post-randomization), will cause the patient to be classified as a "non-responder." Use of *breakthrough* medications as described in Section 4.3.1 will be allowed during this time **with the exception of narcotic analgesics.** 

Therefore, patients will be considered to be "responders" overall for the primary endpoint if they fulfill both of the following two criteria:

1. Report "moderate" or "marked" improvement on the patient-reported global assessment at 34 weeks.

2. Report no increase in pre-study IC medications, and no initiation of new IC medications, and no new or increased use of narcotic medications during the final 4 weeks (weeks 31-34) of the post-treatment follow-up phase.

The proportion of "responders" in each treatment arm will be compared in an intent-totreat analysis to evaluate the overall effectiveness of BCG. Criteria #1 and #2 must both hold for a patient to be considered a responder at 34 weeks; all other patients will be considered "non-responders", and will be included in denominators for evaluation of response rates between treatment arms. Specifically, participants who withdraw from the study for any reason (e.g. adverse event or participant choice) prior to the primary endpoint determination at 34 weeks, will be considered treatment "non-responders."

1219 1220

### 13.2 Sample Size Calculations

1221 1222

1223

1224

1225

1226

1227 1228 The baseline response rate for the intravesical saline placebo of 30% is based on previous IC studies, and other studies suggesting that this is a typical placebo rate for symptom-related outcomes. Assuming 80% power to detect the specified difference between groups at a two-sided  $\alpha = 0.05$  level of significance using the Fisher's exact test, a total of 260 participants (130 per arm) are required. This proposed sample size includes adjustments for clustering within clinical sites (20% increase), and interim monitoring (5% increase). Total required sample sizes for alternative response rate differences are shown in the table below.

## **Sample Size Calculations for 2-arm Study**

Response Rate			Sample Size Per Arm		
Placebo	Treatment	Δ	Before Adjustments	After Adjustments	Total Sample Size
20%	40%	20%	91	115	230
25%	45%		98	124	248
30%	50%		103	130	260
35%	55%		106	134	268
20%	45%		62	78	156
25%	50%	25%	66	83	166
30%	55%		68	86	172
35%	60%		69	87	174
20%	50%		44	56	112
25%	55%	30%	47	59	118
30%	60%		48	60	120
35%	65%		48	61	122
20%	55%	35%	34	43	86
25%	60%		35	44	88
30%	65%		36	46	92
35%	70%		36	46	92

## 13.3 Randomization and Stratification

The nine treating Clinical Centers comprise the nine Clinical Sites. To ensure balance across treatment groups within each Clinical Site, a stratified randomization will be used. Within each of the nine strata, subjects will be randomly allocated in equal proportions to the two treatment arms using a permuted block randomization procedure with variable block sizes. In order to maintain blinding, each subject will be assigned a unique treatment identifier number. The treatment assignment code, corresponding to each treatment identifier number, will be known only to the University of Pennsylvania Medical Center Investigational Drug Service and the Data Coordinating Center Quality Assurance Director, until the completion of treatment and data collection on all

1246 participants.

## 13.4 Intent-to-Treat Analyses and Missing Data

An *intent-to-treat* analysis, in which all available data on all randomized participants are included, will be used for the primary comparison of treatments. All attempts will be made to keep missing data to a minimum, and participants who withdraw from treatment, will be encouraged to continue on study in order to provide complete follow-up information. However, it is expected that up to 15% of the randomized participants may withdraw prior to the final assessment of response at 34 weeks. These participants will be included in the denominator for evaluation of the response rate defined for the primary endpoint. The characteristics at the time of randomization for those participants without complete follow-up will be examined; however, there will be limited statistical power to detect any but major differences between these participants and those with complete follow-up. In addition, in order to assess the potential biases introduced by differential withdrawal among treatment arms, a comparison of withdrawal rates and time to withdrawal will be included as an ancillary analysis to the primary endpoint comparison.

### 13.5 Statistical Analyses

In addition to the analyses described subsequently, descriptive statistics will be used during the course of the project as part of data management procedures for monitoring data quality. A brief overview of some of the statistical methods that may be used at the time of analysis, both for descriptive purposes and in more comprehensive analysis of the primary research questions, is summarized in the following sections. It is recognized that these methods may be revised and additional ones considered as the details of the specific analyses are developed.

### Descriptive Analyses

- 1275 Standard descriptive statistics will be used to describe baseline characteristics and follow-
- 1276 up measures, both overall, and within each treatment group. Examination of baseline
- characteristics will include estimates of the distribution of age, race, and other
- demographic characteristics, baseline severity based upon pain/discomfort, urgency and
- frequency, and Clinical Site. These factors will be examined, both separately for each of

the nine Clinical Sites, and combined across centers. Summary statistics such as means, medians, and ranges will be produced for all measured variables. Frequencies will be computed for all categorical and ordinal variables. Graphical methods including stemand-leaf diagrams and boxplots will be used to examine distributions, identify potential influential points, and guide in the choice of transformations if warranted. The balance of baseline measures across the two treatment groups will be compared using appropriate 2-sample tests, including Fisher's exact tests.

